Patients that cannot be retreated for any reason within 1 week from day 28 (up to day 35) will go off-treatment, unless the investigator believes treatment continuation is in the patient's best

interest. In this case a maximum delay of 2 weeks (up to day 42) will be allowed. Otherwise patients may continue on investigational drug until disease progression, unacceptable toxicity, withdrawal of consent by the patient or other discontinuation criteria described in the protocol are met.

Phase I Dose Escalation

The safety profile of NMS-01940153E administered IV on days 1, 8, 15 every 4 weeks has been characterized in the FIH, dose escalation study, conducted in adult patients with advanced/metastatic solid tumors up to the dose of 135 mg/m²/week. This dose was not defined as MTD in study 2014-002023-10 (EudraCT), since only one patient experienced DLT (Grade 3 fatigue) out of 6 evaluable patients.

Considering the possible different tolerability in patients with compromised liver, the proposed starting dose for the Phase I portion of the study is 100 mg/m²/week, which is an intermediate dose level between the highest (135 mg/m²/week) and the next lower dose level (67.5 mg/m²/week) tested in the FIH study [16]. According to the observed safety profile, dose increments of 25-35% will be applied to the proposed starting dose, until the MTD is reached. In presence of unacceptable toxicity observed at 100 mg/m²/week, a lower dose level by 25-35% may be tested.

Patients experiencing DLT during the DLT window can be retreated according to the time delay and dose modification schema.

No intra-patient dose escalation will be allowed.

Phase II

In the Phase II portion of the study, patients will be treated at the RP2D defined in the Phase I portion as starting dose.

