5.3. Phase II

The Phase I part of the trial ended on May 30th, 2022 with the declaration of an RP2D of 100 mg/m²/week, and the study has already received a unanimous recommendation from an independent Data Safety Monitoring Board (DSMB) to continue the trial, moving to Phase II study.

The RP2D of 100 mg/m²/week, 3 of 4 weekly schedule, is justified based on safety, efficacy and pharmacokinetic considerations. The trend of dose-related neutropenia as the major safety feature points to the 100 mg/m²/week level as more tractable relative to 135 mg/m² (refer to full safety summaries in the IB). In terms of anti-tumor activity, the fact that, out of 6 evaluable, one confirmed RECIST partial response (despite one missed dose during the first two cycles) plus one highly prolonged stable disease were observed at 100 mg/m² as well as, out of 4 evaluable, 2 patients with substantial AFP reduction were observed points to reasonable activity at this dose level. Furthermore, pharmacokinetics at the 100 mg/m² dose level are in a meaningful range relative a continuous mouse tumor stabilization model predicting 0.2 uM average concentration threshold relative to the 100 mg/m² mean Cmax in HCC patients which is 7 fold higher at 1.35 uM and with AUC just slightly below the mouse threshold, 32.5 uM*h versus 35. Refer to IB for full PK descriptions. RECIST response and AFP reductions were observed at the 135 mg/m²/w level and PK was slightly higher but overall the anti-tumor pattern at 135 was similar to 100 mg/m². Therefore, overall, the 100 mg/m² level is justifiable as the RP2D.

In the Phase II portion, patients will receive the RP2D defined in the Phase I portion of the study as starting dose.

As soon as signs of toxicity are observed requiring a dose de-escalation, the dose will be decreased as described in Section 9.2.3.1, Table 6). A maximum of two dose decreases will be allowed, otherwise patient will have to be withdrawn from the study.

Patients will be enrolled in continuous, and continuously evaluated for endpoints, with a futility analysis and stopping criteria for unacceptable toxicity performed as described in Section 12. The enrollment will be stopped in the event of futility as described in Section 12, with no more than 20 subjects treated overall until non-futility can be declared, if appropriate. In any case, the Sponsor may stop or pause enrollments any time during the study based on safety, efficacy or strategic reasons.

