12. STATISTICAL METHODS

12.1. Sample Size Calculation

An overall sample size of approximately 55 patients may be anticipated considering both phases of the study.

For the Phase I, approximately 12-15 treated patients may be expected. Since the trial design foresees that sequential dose-escalation steps are applied to cohorts of 3 to 6 patients up to the identification of the MTD, the number of patients who will be enrolled and treated may vary, depending upon the toxicity observed that will influence cohort size and number of dose levels tested.

For the Phase II, the investigator-assessed objective response rate by RECIST 1.1. will be the primary outcome measure.

The sample size is based on precision considerations for the estimate of the primary efficacy endpoint. A single-group design will be used to obtain a one-sided 95% lower-limit confidence interval for a single proportion. The sample proportion is assumed to be 0.3. To produce a confidence interval with a distance from the sample proportion to the lower limit of no more than 0.12, 38 patients will be needed. A lower bound of 18% for ORR by RECIST would be meaningful relative to second line therapies in HCC. The emergence of atezolizumab with bevacizumab in first line has obscured true current second line outcomes with regorafenib, lenvatinib or sorafenib but it is logical to assume second line ORR would be no better relative to the pre-atezolizumab/bevacizumab era in which sorafenib was the first line standard. Prior to the atezolizumab/bevacizumab era, regorafenib in second line showed ORR of 11% by RECIST1.1 [10] and cabozantinib 4% [22], nivolumab 15% [23], pembrolizumab 18% [24] and apatinib 10.7% [25]. Therefore, in the third line setting following failure of atezolizumab/bevacizumab in first line followed by TKI in second line, and where current third line standards are not yet defined, it is reasonable to expect historical ORR no higher than 18%. Accounting for a 10% proportion of non-evaluable patients and if the stopping rule for futility is not met, up to 43 patients could be required for completing the trial, as reported in detail in Section 12.4; however, the Phase II part of the study will not enroll beyond 40 subjects unless discussed and agreed with FDA or relevant health authority, based on emerging response rates.

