Accumulation ratios for NMS-01940153E and NMS-03593478, based on C_{max} (R_A, C_{max}) and AUC_{last} (R_A, AUC_{last}) will be calculated as the ratio between the individual parameter obtained on Day 15 to the corresponding one on Day 1.

On Day 1 and Day 15, metabolite to parent ratio will be calculated based on C_{max} and AUC_{last} values.

On Day 1 and Day 15, the amount of NMS-01940153E and its metabolite NMS-03593478 excreted in urine in the time interval 0-72 h (Ae₀₋₇₂) will be calculated multiplying the urinary concentration by the urinary volume in the collection times: 0-6, 6-24, 24-48 and 48-72 hours. The parameter will be also expressed as percent of dose (fe%). For the metabolite, the parameter expressed as percent of dose will be calculated after correction of the dose for the molecular weight of the compound.

Renal clearance of NMS-01940153E and its metabolite NMS-03593478 will be calculated as:

$$CLR = Ae_{0-72} / \text{AUC}_{0-72}$$

Statistical analysis

Descriptive statistics (mean \pm SD, CV%, min, max, median) will be calculated for plasma and urine concentration data and pharmacokinetic parameters.

Statistical analysis will be performed after a log-transformation of the data of NMS-01940153E treatment. For each group separately, a mixed effect model will be fitted with day

as fixed effect and subject as a random effect. Day 15 will be compared to Day 1 for each dose level. The ratio will be calculated by back-transforming the difference between the Least Square means. Using the estimate of variance, 90 % confidence intervals will be calculated for the difference and back-transformed. Results of the analyses will be reported in the paragraph of the statistical results.

The power method will be used to evaluate the dose proportionality of NMS-01940153E and possibly its metabolite. C_{\max} , AUC_{last} , AUC_{0-168} and AUC data on Day 1 and Day 15. Dose *versus* C_{\max} and AUC s relationship will be performed using the power model

$$y = a \cdot \text{Dose}^b$$

This relationship becomes linear after a logarithmic transformation

$$\log(y) = \log(a) + b \cdot \log(\text{dose})$$

where a is the intercept to y (AUC) axis and b is the slope of the regression line. Dose proportionality required slope to be close to unity for dose dependent parameters, and decision on dose proportionality will be made based on the inclusion of the theoretical slope of 1 in the 90 % confidence intervals.

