2. PURPOSE OF THE STATISTICAL ANALYSIS PLAN

This Statistical Analysis Plan (SAP) version 2.0, describes the planned Phase I analysis, Phase II interim and final analyses and reporting for MPSA-153-001 Clinical Trial (CT). All analyses take origin from the specifications in the statistical section of the CT Protocol version 5.0 (9-Jan-2023). Details of changes of the SAP version 2.0 respect to the first version, created based on CT Protocol version 2.0 dated 28-Jan-2021, are reported in Section [2.1](#).

Of note, this SAP does not cover the pharmacokinetic (PK) data analyses, described in the Protocol. These analyses are covered in a separate document written by Accelera S.r.l.

The structure and content of this SAP provide sufficient detail to guarantee compliance with the requirements identified by the International Conference on Harmonisation of Technical Requirements for Registration of Pharmaceuticals for Human Use (ICH): E9 Guidance on Statistical Principles in Clinical Trials and Integrated Addendum to E9(R1) [\[1\]](#).

The planned analyses identified in this SAP may be included in future abstracts, presentations and manuscripts, and may also support other documents, e.g. Development Safety Update Report (DSUR). Exploratory analyses not necessarily identified in this SAP may be performed to support planned analyses. Any post-hoc or unplanned analyses not specified in this SAP will be clearly identified as such in the Clinical Study Report (CSR).

The following documents were reviewed when preparing this SAP:

- CT Protocol version 5.0 (09-Jan-2023)
- CT Specific Case report forms (CRFs) Blank version 5.3 (23-Jun-2023)
- E9 - Statistical Principles for Clinical Trials [Integrated Addendum to E9(R1)] [\[1\]](#)
- E6(R2) - Guidance on Good Clinical Practice [Integrated Addendum to E6(R1)] [\[1\]](#)
- E3 - Guidance on Structure and Content of Clinical Study Reports [\[1\]](#)
- Applicable NMS procedural documents

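### Phase I dose proportionality is decided by whether the 90% CI for the power-model slope contains 1, a rule that imprecise data pass more easily than precise data

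*Protocol*

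**What the plan says.** Protocol Section 12.3.7.2.1 regresses log exposure (Cmax, AUClast, AUC0-168 and AUC, on Day 1 and Day 15) on log dose. The sentence on interpretation has two parts. The first is "Dose proportionality required slope to be close to unity for dose dependent parameters". The second is the operative rule: "decision on dose proportionality will be made based on the inclusion of the theoretical slope of 1 in the 90 % confidence intervals". No numeric limit is attached to closeness, and no cap is placed on the width of the interval.

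The SAP does not add to this. Its Section 2 takes PK out of scope: "These analyses are covered in a separate document written by" the PK contractor. That document was not available for this review.

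Three design features bear on precision:

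- On dose steps, Protocol Section 5.1 says "dose increments of 25-35% will be applied to the proposed starting dose, until the MTD is reached".
- On numbers, Section 12.1 says "For the Phase I, approximately 12-15 treated patients may be expected", in cohorts of 3 to 6.
- Section 5.3 reports results at 100 and 135 mg/m² only. It gives means without any SD or CV, for example a "mean Cmax in HCC patients which is 7 fold higher at 1.35 uM".

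**The concern.** A confidence interval that contains 1 shows only that the data do not contradict proportionality. A wide interval contains 1 along with slopes that would mean no rise in exposure, or a rise far steeper than the dose. Used as a decision rule, inclusion of 1 therefore rewards imprecision, and a small Phase I over a narrow dose range is where imprecision is expected.

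PK parameters are a secondary endpoint, and the report could carry a statement of dose proportionality that the data cannot support. The stakes stop there. Phase I ended on May 30th, 2022 with the RP2D declared, and the comparison of exposure at the two levels in Section 5.3 is a single descriptive clause ("PK was slightly higher but overall the anti-tumor pattern at 135 was similar to 100").

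**Working it through.** The plan states no power or error rate for this analysis, so there is no figure of its own to reproduce.

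**Inputs from the documents.** The decision rule (Protocol 12.3.7.2.1); 12 to 15 Phase I patients (12.1); reported levels of 100 and 135 mg/m² (5.3), so a dose ratio of 1.35 and ln(1.35) = 0.300.

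**Assumptions.** Only these two levels; 6+6 or 7+8 patients; dose in mg/m²; between-patient CV of 20% to 60%; one parameter on one day.

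**Formulae.** With x = ln(dose), the residual SD is s = √ln(1+CV²) and SE(b) = s/√Sxx, on n−2 df. The rule passes when |b̂ − 1| is less than t(0.95, n−2) times the estimated SE. Its probability follows from the noncentral t distribution with noncentrality (b−1)/SE(b).

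**Worked case (6+6, CV 40%, true slope 2).** Sxx = 12 × (0.300/2)² = 0.270. s = √ln(1.16) = 0.385. SE = 0.385/√0.270 = 0.741. The critical t on 10 df is 1.812, and the noncentrality is 1/0.741 = 1.35. The chance that the interval contains 1 is 0.649. By symmetry a true slope of 0 gives the same figure. A slope of 2 means exposure multiplied by 1.35² = 1.82; a slope of 0 means no rise.

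**Across the CV range:**

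| | CV 20% | 30% | 40% | 50% | 60% |
|---|---|---|---|---|---|
| Mean 90% CI half-width, 6+6 | 0.67 | 1.00 | 1.31 | 1.61 | 1.89 |
| Mean 90% CI half-width, 7+8 | 0.59 | 0.88 | 1.15 | 1.42 | 1.66 |
| Pass rate, slope 1 (any layout) | 90% | 90% | 90% | 90% | 90% |
| Pass rate, slope 0 or 2, 6+6 | 21% | 50% | 65% | 73% | 77% |
| Pass rate, slope 0 or 2, 7+8 | 13% | 41% | 59% | 68% | 74% |
| Pass rate, slope 0.5 or 1.5, 6+6 | 66% | 79% | 83% | 86% | 87% |
| Pass rate, slope 3, 6+6 | 0.1% | 5% | 19% | 34% | 46% |

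The pass rate for slope 0 or 2 reaches one half at a CV of about 30% with 12 patients and 34% with 15. A slope of 0.5 or 1.5 passes 51% of the time even at CV 15% (6+6).

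**Dependence on n (CV 40%, slope 2, equal groups).** 79% with 6 patients, 65% with 12, 42% with 24 and 16% with 48. Fewer data make the favourable conclusion more likely.

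**Layouts in which the problem is smaller (slope 2, CV 20/30/40/50/60%):**

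- A third level (100/135/182 mg/m², 6+6+3 patients): 1/12/31/46/56%.
- Total mg as the regressor, with an assumed BSA CV of 10% (simulated): 13/39/57/66/73% with 12 patients and 7/30/49/60/68% with 15.

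**The case against.** The strongest reply is that the sentence also requires a slope close to unity. Read as a joint condition with a numeric limit, this would cut the error sharply. With an assumed limit of ±0.25 to ±0.75, slope 2 at 6+6 passes in 11-36% of trials at CV 40%, instead of 65%. But the protocol gives no such number, so the clause constrains nothing as written. If the separate PK document supplies one, the concern shrinks accordingly.

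The lead scenario is also an unfavourable one. The plan left the number of levels open, the number treated at 135 mg/m² is not reported, and dose may mean total mg. This is fair, and it is why the other layouts are shown. They reduce the rates without changing the logic of the rule.

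Dose proportionality is itself named in no objective or endpoint, the Phase II dose is fixed, and Phase II PK uses a population model. That stands, and it limits the weight of the point. Finally, the undefined meaning of dose and the lack of a rule for combining four parameters over two days are missing detail. The wording can be read as parameter by parameter, and the conclusion does not rest on either gap.

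**Conclusion.** The concern holds. The rule treats non-rejection of slope 1 as a positive conclusion, and nothing in the protocol or SAP stops a wide interval from producing it. That much needs no assumption. The size does depend on assumptions, above all on a CV the documents do not give. With two levels at 100 and 135 mg/m² and 12 to 15 patients, a slope of 0 or 2 is called proportional in anything from 13% (CV 20%, 15 patients) to 77% (CV 60%, 12 patients) of trials. A third dose level lowers this to between 1% and 56%. The consequence is confined to one secondary PK statement, so the rule should be changed, but it does not threaten the primary endpoints or the dose already chosen.

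**What to change.** First check the separate PK analysis document for further criteria. If it has none, replace the decision sentence in Protocol 12.3.7.2.1 with text along these lines:

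> For each parameter and day, the slope, its 90% CI, and the dose-normalised geometric mean exposure ratio (highest versus lowest dose) with its 90% CI will be reported. Inclusion of 1 in the CI will not by itself be taken as evidence of dose proportionality.

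State in the same place whether dose is mg/m² or total mg. No verdict is needed. If one is wanted, conclude proportionality only when the whole CI lies within pre-stated limits, and otherwise report the result as inconclusive. One possible choice, assumed here and not taken from the documents, is 1 ± ln(1.25)/ln(r). For r = 1.35 this is 1 ± 0.744, or 0.26 to 1.74.

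The cost is one sentence and no new data. The change should be dated and described as made after Phase I PK results were seen. The report loses a yes/no statement. Under the example limits, a truly proportional drug would qualify in only 20-34% of trials at CV 20%, 2-3% at CV 30% and 0.3% or less at CV 40% and above. Inconclusive would then be the likely result, because a study of this size over so narrow a dose range can rarely establish proportionality.

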12.3.7.2.2. Phase II

For PK plasma samples collected during Phase II, a sparse sampling procedure will be adopted. For each patient, a total of 20 plasma samples will be collected; the blood sample intervals are designed to patients to grant homogeneous distribution of the samplings in different time intervals (refer to [Table 14](#)).

Pharmacokinetic data from Phase II portion of the study will be analyzed using mixed-effect modeling approach. Data may be also pooled with PK data from previous Phase I studies.

Details of the sampling procedures as well as population PK model development description and population PK data analysis will be detailed in the population PK Statistical Analysis Plan.

The objective of the population pharmacokinetic data analysis will be to describe the pharmacokinetics of NMS-01940153E in the subject population and explore the role of demographic and pathophysiological covariates influencing the pharmacokinetics of the compound. The main pharmacokinetic parameters and the influence of covariates (e.g., gender, age, body weight, histopathological covariates) will be estimated using a population PK approach. The key guidances of FDA and EMA will be followed in the population PK analysis. The population PK analysis will be performed using NONMEM software (version VII or higher).

The population PK model will consist of the following:

- identification of the structural model that best describe the pharmacokinetic data in absence of covariates.
- Identification of the variance component/s characterizing between-patient variability (BSV) in model parameters. The between-patient variability (BSV) will be modeled as an exponential random-effect model in order to positively constrain the individual parameter values, which will be thus assumed to follow the following log-normal distribution:

$$\theta_i = \theta_{\text{Typical}} \cdot \exp(\eta_i)$$

where θ_i is the PK parameter for the i th individual, θ_{Typical} is the typical value (geometric mean) of the parameter in the population, η_i is a random inter-patient effect with mean 0 and estimated variance ω^2 .

- Residual unexplained variability will be modeled using additive or proportional or additive and proportional models, or other error models considered suitable. The residual error $\varepsilon_{i,j}$ will be assumed to be normally distributed with mean 0 and the variance σ^2 .

12.3.7.2.3. Covariate Analysis

Covariate analysis will be performed using visual inspection in order to identify relevant covariates explaining the variability of NMS-01940153E. The most relevant covariates will be then formally evaluated using a stepwise forward additive approach using a p-value of 0.05 and a backward elimination using a p-value of 0.01 (chi-squared distribution).

12.3.7.3. Translational Research

Exploratory analyses on biomarkers in blood and tumor will be conducted based on the completeness of data collected.

12.4. Interim Analysis Plan

In the Phase II part of the study an interim evaluation for futility will be undertaken as soon as the first 10 evaluable patients will be enrolled and the data for primary efficacy endpoint analysis will be available including observations through at least 3 months with at least 1 on-treatment tumor assessment by RECIST 1.1. If less than 1 responder i.e., patients who achieved CR or PR as best overall response, are observed, the study will be terminated for futility. This futility decision must be taken before 20 subjects total are enrolled otherwise enrollment will pause at 20 subjects until non-futility can be declared (if applicable). If at least 1 unconfirmed or confirmed responder is observed and there are no safety limitations, patients' enrollment will continue and proceed up to an overall enrollment of 38 evaluable patients or 40 total patients. For the safety monitoring, if two or more patients on study experience Grade 4 adverse events the study will be put on hold to evaluate whether to continue or if additional risk mitigation is warranted. The independent DSMB will review the interim results and provide a recommendation on the study progress.

Notification of the temporarily interruption of recruitment as well as restart of enrollment will be notified to the IECs.

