11.3.1. Tumor Imaging

Baseline tumor imaging (by CT scan, PET or MRI) has to be performed at screening within 28 days prior to the treatment start. On treatment, tumor assessments will be performed every even month (i.e., end of Cycle 2, 4, 6 etc) or whenever a clinical deterioration is observed and at the end of last cycle, unless a tumor assessment was performed within the previous 4 weeks. In patients withdrawn for causes other than disease progression, during follow up, regular tumor imaging assessments will be performed every 2 months, until PD or until a new antitumor therapy starts. On treatment, a time window of -2/+5 days is allowed.

Patients with responding tumors (complete or partial response) must have response confirmed at least 4 weeks after the first documentation of response.

CT scan is the desirable method for lesion measurement. MRI is acceptable provided that the size of the measurable lesion is twice the slice thickness of the MRI. MRI should be performed at pre-treatment in case of known or suspected CNS involvement.

According to RECIST, the same method and technique (CT scan or MRI) should be used to characterize each identified and reported lesion at baseline and during the following assessments.

Imaging-based evaluation should be preferred to clinical examination when both could be used to assess the antitumor effect of the treatment.

According to mRECIST, tumor assessment should be performed with the administration of intravenous contrast to obtain a dual-phase imaging of the liver. To prevent possibly allergic reactions to intravenous Contrast Medium (CM), patients with previous reaction(s) to CM, asthma even drug controlled and/or food or drug allergies will be treated with a premedication (corticosteroid).

Patients can be followed with either contrast-enhanced spiral CT (preferably with use of multi-slice scanners) or contrast-enhanced dynamic MRI. Each modality has advantages and disadvantages, and mRECIST does not recommend one modality over another.

However, it is recommended that the same imaging modality be used throughout the study. Ultrasound – including contrast-enhanced ultrasound – is not recommended for the general use of mRECIST.

PET/CT is not accepted for treatment assessment in guidelines.

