11.3.1.10. Best Overall Response

The best overall response is the best response recorded from the start of the study treatment until the end of treatment taking into account any requirement for confirmation (achievement of both measurement and confirmation criteria, depending on the nature of the study and the protocol requirement). The patient's best overall response assignment will depend on the findings of both target and non-target disease and will also take into consideration the appearance of new lesions.

Table 11. Best overall response when confirmation of CR and PR required

Overall response First time point	Overall response Subsequent time point	BEST overall response
CR	CR	CR
CR	PR	SD, PD or PR ^a
CR	SD	SD provided minimum criteria for SD duration met, otherwise, PD
CR	PD	SD provided minimum criteria for SD duration met, otherwise, PD
CR	NE	SD provided minimum criteria for SD duration met, otherwise NE
PR	CR	PR
PR	PR	PR
PR	SD	SD
PR	PD	SD provided minimum criteria for SD duration met, otherwise, PD
PR	NE	SD provided minimum criteria for SD duration met, otherwise NE
NE	NE	NE

CR = complete response, PR = partial response, SD = stable disease, PD = progressive disease, and NE = not evaluable.

^a If a CR is truly met at first time point, then any disease seen at a subsequent time point, even disease meeting PR criteria relative to baseline, makes the disease PD at that point (since disease must have reappeared after CR). Best response would depend on whether minimum duration for SD was met. However, sometimes 'CR' may be claimed when subsequent scans suggest small lesions were likely still present and in fact the patient had PR, not CR at the first time point. Under these circumstances, the original CR should be changed to PR and the best response is PR.

In some circumstances, it may be difficult to distinguish residual disease from normal tissue. When the evaluation of a CR depends upon this determination, it is recommended that the residual lesion be investigated by fine needle aspirate or biopsy before assigning a status of CR.

For equivocal findings of progression (e.g., very small and uncertain new lesions; cystic changes or necrosis in existing lesions), treatment may continue until the next scheduled assessment. If at the next scheduled assessment, progression is confirmed, the date of progression should be the earlier date when progression was suspected.

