5.2. Planned Schedule of Interim Analyses

In the Phase II part of the study an interim evaluation for futility will be undertaken as soon as the first 10 evaluable patients will be enrolled and the data for primary efficacy endpoint analysis will be available including observations through at least 3 months with at least 1 on treatment tumor assessment by RECIST 1.1 [2]. If less than 1 responder i.e., patients who achieved CR or PR as best overall response, are observed, the study will be terminated for futility. This futility decision must be taken before 20 subjects total are enrolled otherwise enrollment will pause at 20 subjects until non-futility can be declared (if applicable). If at least 1 unconfirmed or confirmed responder is observed and there are no safety limitations, patients' enrollment will continue and proceed up to an overall enrollment of 38 evaluable patients or 40 total patients. For the safety monitoring, if two

or more patients on study experience Grade 4 adverse events the study will be put on hold to evaluate whether to continue or if additional risk mitigation is warranted. The independent DSMB will review the interim results and provide a recommendation on the study progress.

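### The 0-of-10 futility stop can be taken before later-enrolled patients have had their Cycle 4 scan, which modestly raises the chance of stopping an active drug

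*Protocol*

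**What the plan says.** Protocol 12.4 schedules the interim "as soon as the first 10 evaluable patients will be enrolled" and their primary-endpoint data are available, "including observations through at least 3 months with at least 1 on-treatment tumor assessment by RECIST 1.1". Protocol 1.4 (Interim Analyses) repeats this, and SAP 5.2 has the same condition: "including observations through at least 3 months with at least 1 on treatment tumor assessment by RECIST 1.1". If fewer than one patient has CR or PR as best overall response, the consequence is stated without qualification: "are observed, the study will be terminated for futility". The trial goes on "If at least 1 unconfirmed or confirmed responder is observed and there are no safety limitations". If the decision is late, "otherwise enrollment will pause at 20 subjects until non-futility can be declared".

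Two other sections fix what can be known by then. Protocol 11.3.1 sets the scans: "tumor assessments will be performed every even month (i.e., end of Cycle 2, 4, 6 etc", with a window of -2/+5 days. Protocol 11.3.1.10 defines the endpoint: "The best overall response is the best response recorded from the start of the study treatment until the end of treatment". No section gives a status for a patient who is on drug, has not progressed and has not yet responded when the interim is read.

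**The concern.** The stop uses an endpoint that stays open until treatment ends, but the maturity condition can be met after a single scheduled scan. For a patient without a response at the Cycle 2 scan, waiting from that scan to month 3 adds no scheduled tumor information. Such a patient, stable and on drug, is counted like one who has progressed. A response first seen at Cycle 4 would count in the final ORR but cannot count at the interim for the last patients enrolled.

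This is the only efficacy rule that ends Phase II. Taken alone, the immaturity works in one direction: it makes a stop more likely when the drug is active.

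**Working it through.** **The plan's own figures.** The assumed ORR of 0.30 comes from the sample-size section (Protocol 12.1, SAP 4.3). Its 38 patients reproduce: with the exact (Clopper-Pearson) one-sided 95% lower limit, the distance from 0.30 at n = 38 is 0.1197, within the stated 0.12. The plan gives no operating characteristics for the 0-of-10 rule. If every response were observable, the false-stop probability would be 0.70^10 = 2.8%.

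**Timing.** Cycles last 28 days (Protocol 9.2.1).
- Scan 1: day 56, window 54 to 61.
- Scan 2: day 112, window 110 to 117.
- Three months: 3 x 30.4 = about day 91, which is 110 - 91 = 19 to 117 - 91 = 26 days before scan 2.

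**Who has only one scan.** Suppose the decision is taken when patient 10 reaches day 91 and accrual is even at r per month (an assumption; the documents state no rate). Patient k then has follow-up of 91 + 30.4 x (10 - k)/r days. The number of the ten below day 112 is 1, 2, 3, 4 and 7 at r = 1, 2, 3.3, 5 and 10. The rate of 3.3 per month is the one at which ten further patients enrol in three months (10/3), so that the pause at 20 just binds.

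**False-stop probability at ORR 0.30.** Multiply over the ten patients (1 - 0.30 x share of responses visible by that patient's follow-up), with scans at days 56, 112 and 168. The timing of first response is assumed. Example at 3.3 per month with 65/25/10% at scans 1/2/3: three patients have one scan, six have two and one has three.
- As written: (1 - 0.195)^3 x (1 - 0.27)^6 x 0.70 = 5.5%.
- With scan 2 required for all: (1 - 0.27)^9 x 0.70 = 4.1%.

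| First response at scans 1/2/3 | Accrual per month | As written | Cycle 4 scan required | Gain (points) |
|---|---|---|---|---|
| 65/25/10% | 2 | 4.4% | 3.6% | 0.8 |
| 65/25/10% | 3.3 | 5.5% | 4.1% | 1.4 |
| 65/25/10% | 5 | 6.4% | 4.3% | 2.1 |
| 50/30/20% | 2 | 5.8% | 4.6% | 1.2 |
| 50/30/20% | 3.3 | 8.3% | 5.9% | 2.4 |
| 50/30/20% | 5 | 10.1% | 6.4% | 3.7 |

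If 80% of responses appear at scan 1 (split 80/15/5), the as-written figures are 3.6 to 4.5% over the same rates, and the gain is about 1 point or less. If all ten start almost together, the as-written figures are 11.4% (65/25/10) and 19.7% (50/30/20), falling to 4.3% and 6.4%. The column for the required scan gives earlier patients no credit for follow-up gained during the wait, so it is slightly conservative.

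**The case against.** Several points on the other side are sound.

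- **Unconfirmed responses pass.** The ORR of 0.30 is for confirmed response, yet one unconfirmed response keeps the trial open. The model leaves out responses that later fail confirmation. If, as an illustration, 3% of patients had one at scan 1, the 5.5% above would fall to 3.7%. This lowers the excess, but it does not help a patient whose response is first visible at Cycle 4.
- **Three months is a minimum and has a logic.** The latest first scan (day 61) plus the 4 weeks for confirmation is day 89. But the rule does not need confirmation to pass, so that wait does nothing for a patient without a response at scan 1. The requirement that endpoint data be available could be read as asking for more, but the same sentence then sets the minimum at 3 months and one scan.
- **Decisions take time.** A three-week lag for reading and review (assumed), with new scans counted, would bring 5.5% down to 3.8% without any amendment. The plan does not require such scans to be counted.
- **The DSMB reviews the interim.** It recommends on study progress, on a risk-benefit basis (Protocol 12.5, SAP 5.1), and would see the patients who are stable on drug. No power to defer the stop is stated.
- **Enrolment pauses at 20.** This limits exposure; it does not make the stop wait.

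A reader might infer that the rule carries a false-stop risk of 11 to 20%, or that a longer wait would restore 2.8%. The documents support neither. The first needs near-simultaneous enrolment, which nothing in the plan suggests. The second needs every response to be visible by Cycle 4.

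**Conclusion.** The point holds as a modest, inexpensive improvement. Followed exactly, the plan permits a zero-responder stop while some of the ten have had one scheduled scan and have an open best overall response. At true ORR 0.30 the false-stop probability is then about 4 to 6% or 6 to 10%, according to the response timing assumed, at 2 to 5 patients a month. Requiring the Cycle 4 scan recovers roughly 1 to 4 points. The gain is smaller with slower accrual or mostly early responses, and larger only with very fast accrual.

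These sizes rest on assumed accrual and response timing, an ORR of 0.30, and a decision exactly on day 91. Unconfirmed responses and any decision lag would reduce the excess. It would go too far to say that the interim rule as a whole can only err towards stopping: that is true of the immaturity alone, because passing on a single unconfirmed response pulls the other way.

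**What to change.** Add to Protocol 1.4, Protocol 12.4 and SAP 5.2:

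*If no responder has been observed when the interim criteria are met, the study is terminated for futility only once each of the first 10 evaluable patients has had the end-of-Cycle-4 tumor assessment or has progressed, died or permanently discontinued. From the time the interim criteria are met until then, enrolment is paused; before that time the existing limit of 20 subjects applies unchanged.*

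The decision to continue on at least one unconfirmed or confirmed responder stays as it is. Tying the pause to the interim trigger matters: a pause that began earlier would override the plan's permission to enrol up to 20 while data mature.

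The cost is two sentences in each place. No scan is added, because the Cycle 4 scan is already scheduled, and no further patient is enrolled during the wait. In the zero-responder case only, the decision and enrolment are delayed by about 3 to 4 weeks, or about 6 weeks if a patient has three one-week cycle delays (112 + 21 - 91 = 42 days). The change reduces the immaturity of best overall response at the interim but does not remove it: a patient still stable after Cycle 4 would count as a non-responder.
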